In determining the sample size of 218 needed to recruit for the study, we examined the number of patients needed to have adequate power to detect differences between the intervention and usual care groups using the mean DDS17 score as the primary outcome. The sample size was initially based on testing for a medium effect size ($d = .50$) between the intervention and usual care groups at a single time point, using a two-group t test with a 0.05 2-sided significance level and power of 80%. Because we will assess participants at three time points (baseline, posttreatment, and 6 months), this estimate was then adjusted to account for the correlation among the repeated measurements, using the adjustment factor $[1 + (T-1)\bar{\rho}]/T$, where T is the number of follow-up measurements and $\bar{\rho}$ is the correlation coefficient of the repeated measurement. In our study, $T = 2$ follow-up measurements after baseline, and $\bar{\rho}$ is estimated using the relatively high value of 0.5. The sample size determined for the primary outcome was inflated to account for attrition of 30% at 6 months. In a VHA-funded investigator-initiated grant (Behavioral Activation Therapy for Rural Veterans with Diabetes and Depression; PI: [name]), on which members of the research team are co-investigators, attrition at 6 months was 16.9%. Because this study will include Veterans from VHA and non-VHA settings, we estimated attrition to be somewhat higher than what we

found in the study of patients from VHA settings only. Thus, a sample size of 134 patients would need to be recruited (67 in the intervention group and 67 in usual care) for 80% power to find important differences in the DDS17 measures.

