Outcomes: Primary outcome. We will compare participants in the 2 study arms on baseline characteristics, including sociodemographic characteristics and clinical variables. Based on the Consolidated Standards of Reporting Trials recommendations, we will not provide tests of significance or adjust subsequent analyses for variables found to differ because adjustment may bias the estimated treatment effect. However, because socioeconomic status (SES) and race/ethnicity might impact the mechanism of navigation/coaching, we will include the SES (income and education) and race/ethnicity variables as a priori covariates in our regression analyses. We will examine distributions of the primary outcome (DDS17) and consider transformations, if necessary. We will test for differences between the active intervention and usual care groups using continuous dependent measures (either untransformed or transformed if needed). The random coefficient model will allow us to fit a line for each participant using his/her available data, including participants with missing values, and will maximize the power to detect differences because participants are not removed from the analysis if any time period is missing. Analyses will contain a variable indicating the treatment group, a variable representing the referral source (MEDVAMC and non-MEDVAMC [community social service agencies, or VSOs]), SES and race/ethnicity variables, a variable indicating time (baseline, 3 months, or 6 months), and a term for the interaction of time and treatment. The time-by-treatment interaction is of most interest in this repeated measures analysis because a significant value will indicate a difference between groups over 6 months.

The treatment effect will measure differences between the groups at baseline, and the time effect will measure outcome change over time. By dichotomizing the outcome, we will determine whether the groups differed proportionally in clinically significant improvement on the DDS17. A value of 2.9 or less for the DDS17 will be considered as indicating little or no distress to moderate distress; a value of 3.0 or more will represent high distress. We will test this difference using a logistic regression model in which the dichotomous outcome is the dependent variable. Independent variables will be those for the linear regression models.

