Outcomes: Secondary outcomes. Analyses of the secondary clinical outcomes will be similar to those used for the continuous primary outcomes. We will test assumptions of normality and make transformations as needed. We will then run linear regression models separately for each secondary outcome. The models will include terms for the intervention, time period, time-by-period interaction, the a priori SES and race/ethnicity variables, and the referral source. Significant values for the time-by-treatment interaction will indicate that there were significant differences over time in the secondary outcome. In addition, by dichotomizing the outcomes, we will determine whether the groups differed in having or not having clinically significant changes in PHQ-8 and GAD-7 scores. A 5.0-point decrease in the value of PHQ-8 will be considered a minimally clinically important change⁹⁴ and coded as such; decreases of less than 5.0 points from baseline will be coded as not having achieved clinically significant change. For GAD-7, a score of less than 10 will be considered as having clinical improvement, with scores of 10 or higher representing clinically elevated anxiety symptoms. We will test whether the two groups (clinically significant change vs. no clinical change) differed using a logistic regression model in which the dichotomous outcomes are the dependent variable. The independent variables will be those described above for the linear regression models.

For the secondary outcomes of use of printed/web-based resources, health promotion programs, and clinical care, we will run logistic regression analyses of dichotomized variables (i.e., whether or not the patient used printed/web resources, whether or not he/she used health promotion programs, and whether or not he/she used clinical care during the 6-month follow-up). The models will include terms for the intervention, the a priori SES and race/ethnicity variables, and the referral source. Significant values for the treatment term will indicate that there were significant differences between the iNSPiRED and usual care groups.

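### The primary model gives each arm its own baseline DDS17 mean, so the interaction test draws less precision from baseline than an adjusted analysis would: about 5 points of power at month 6 if the baseline correlation is 0.5

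*Combined protocol and SAP*

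**What the plan says.** Section G2 (Primary outcome) describes a random coefficient model that fits a line for each participant and keeps those with missing visits. Its terms are treatment group, referral source, SES, race/ethnicity, and "a variable indicating time (baseline, 3 months, or 6 months), and a term for the interaction of time and treatment". The interaction is the term of interest. The section then interprets the other terms: "The treatment effect will measure differences between the groups at baseline, and the time effect will measure outcome change over time".

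Baseline DDS17 is thus a response, not a covariate, and nothing constrains the arms to a common baseline mean. No baseline-adjusted sensitivity analysis is described. G2 does decline one kind of adjustment, but that refusal concerns variables that turn out to differ between arms. It does not concern the prespecified baseline value of the outcome.

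The continuous secondary outcomes follow the same pattern: "The models will include terms for the intervention, time period, time-by-period interaction, the a priori SES and race/ethnicity variables, and the referral source". I read the interaction there as time-by-treatment, as the next sentence of that section does.

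**The concern.** In a randomised trial, any difference in mean baseline DDS17 between arms is due to chance. A model that estimates that difference freely subtracts it in full from the follow-up difference. A model that adjusts for baseline, or holds the two baseline means equal, subtracts only the part that baseline predicts, which is rho times the imbalance (rho being the baseline-to-follow-up correlation). The second estimator has the smaller variance whenever rho is below 1.

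At stake are the width of the interval and the power for the primary question, and likewise for the continuous secondary outcomes. G2 presents its model as one that maximises power, so an avoidable loss runs against the plan's own aim.

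**Working it through.** **Inputs (Section G1 unless stated).**
- Effect: "testing for a medium effect size ($d = .50$) between the intervention and usual care groups at a single time point", taken here as the month-6 effect in SD units; two-sided 5%, 80% power.
- T = 2 "follow-up measurements after baseline".
- Correlation: it "is estimated using the relatively high value of 0.5". G1 uses this only in its repeated-measures factor. Applying it between baseline and follow-up is my assumption, ranged below.
- Attrition: sample size "inflated to account for attrition of 30% at 6 months".
- 218 enrolled, 1:1 (Section F1): N = 109 per arm, n = 0.7 × 109 = 76.3 with follow-up, m = 32.7 with baseline only.
- Also assumed: equal variances, equal correlation at all lags, and loss before month 3. A fitted random slope would change the figures somewhat.

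**The plan's own figure.** 2(1.960 + 0.842)²/0.5² = 62.79 per arm. Multiplied by [1 + 0.5]/2 = 0.75 this is 47.09; divided by 0.7 it is 67.3. G1 states 67 per arm, 134 in total, so it reproduces.

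**Month-6 contrast, all available data.** Variance of the between-arm estimate:
- Separate baseline means (as planned): 2[(1 − rho²)/n + (1 − rho)²/N] = 2[0.75/76.3 + 0.25/109] = 0.02425, SE 0.1557. Power = Φ(0.5/0.1557 − 1.96) = **89.5%**.
- Common baseline mean: 2(1 − rho²)/n = 2 × 0.75/76.3 = 0.01966, SE 0.1402. Power = Φ(0.5/0.1402 − 1.96) = **94.6%**.
- Loss 5.1 points; the variance ratio is 0.01966/0.02425 = 0.81.

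**Mean of months 3 and 6 (effect 0.5 at both).** The residual variance given baseline is (1 + rho)/2 − rho² = 0.50.
- Separate: 2[0.50/76.3 + 0.25/109] = 0.01769, power 96.4%.
- Common: 2 × 0.50/76.3 = 0.01311, power 99.2%.
- Loss 2.8 points, or 2.1 if half of the attrition comes between months 3 and 6.

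**Straight-line slope (effect rising to 0.5 at month 6).** With time scaled 0, 0.5, 1 and rho = 0.5, each completer contributes information 1.5 (intercept), 0.75 (cross term) and 1.375 (slope).
- Separate intercepts: 2/[1.375n − (0.75n)²/(1.5n + m)] = 2/[104.91 − 22.25] = 0.02420, power 89.5%.
- Common intercept: 2/(1.375n) = 2/104.91 = 0.01906, power 95.2%.
- Loss 5.7 points, or 5.8 with the later dropout. If the effect is already 0.5 at month 3, the loss is 6.7 (5.7 with the later dropout).

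**Sensitivity of the month-6 result to rho.**

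| rho | As planned | Common baseline | Loss (points) |
|---|---|---|---|
| 0.3 | 78.8% | 89.9% | 11.1 |
| 0.4 | 84.0% | 92.1% | 8.0 |
| 0.5 | 89.5% | 94.6% | 5.1 |
| 0.6 | 94.5% | 97.1% | 2.6 |
| 0.7 | 98.3% | 99.1% | 0.8 |

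Losses come from unrounded powers, so they can differ by 0.1 from the differences shown.

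**The case against.** The planned model is standard and valid. It controls type I error, and chance imbalance is removed by subtraction, so the estimate is not biased. The plan aims for 80% power, and at 218 it has more than that for the primary outcome when rho is 0.5. All of this stands.

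Three stronger readings are tempting, and the documents do not support them.

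- **A loss of 5 to 8 points.** A reader might compute this from completers alone: at rho = 0.5, 87.0% v 94.6% at month 6 and 94.6% v 99.2% for the two-visit mean. G2 keeps participants with missing visits, and the baseline rows of those lost recover part of the precision. The completer figures describe an analysis that is not planned. For the same reason it is too strong to say that baseline buys nothing at rho = 0.5. That equality, 2(1 − 0.5) = 1, holds only for complete data at a single visit.
- **An underpowered trial.** A reader might point to month-6 power at 134 enrolled, about 68% for a completer change contrast. G1 raises enrolment to 218. Even at 134, the two-visit mean change has variance factor 0.75 + 1 − 2(0.5) = 0.75, which is G1's own planning factor, so that contrast keeps about 80%.
- **A correlation below 0.5 caused by selecting on distress.** Entry is on the two-item screen, not the DDS17, and the documents give no figure for its effect on the correlation.

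One objection bears on the remedy. A common baseline mean is safe only if DDS17 is recorded before allocation is known. F2 places randomisation upon consent, and J1a places consent before the baseline measures, but neither puts randomisation after baseline. F1 calls the baseline assessment preintervention, and F2 has an evaluator without access to assignment. Neither establishes that the participant, who supplies the self-report, is unaware of the arm. The planned model does not rest on that assumption.

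**Conclusion.** The point holds as an efficiency improvement. The primary model leaves the arms' baseline means free, so its interaction test gains less from baseline DDS17 than an adjusted analysis of the same data would. At 218 enrolled, d = 0.5, 30% attrition and rho = 0.5, the cost is about 5 points of power at month 6, 2 to 3 for the mean of the two follow-up visits and about 6 for the slope.

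The size depends on a baseline-to-follow-up correlation that the documents do not give. The loss is negligible at 0.7 and substantial at 0.3, where planned month-6 power falls just under 80%. There is no bias, and at rho = 0.5 the planned power is met.

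**What to change.** First confirm, and state in F2, that baseline DDS17 is completed before allocation is known to the participant and the assessor. If that is so:

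1. In G2 (Primary outcome), keep the random coefficient model but drop the treatment main effect, leaving time, time-by-treatment, referral source, SES and race/ethnicity. If time is fitted as three categories, define the interaction at months 3 and 6 only. Otherwise the software may put the baseline difference back inside the interaction.
2. Delete the sentence that has the treatment term measure baseline differences.
3. Use the same form for the continuous secondary outcomes.

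An alternative is to model DDS17 at months 3 and 6 with baseline DDS17 as a covariate, treatment and treatment-by-visit being the tested terms. Under dropout this is close but not identical, because participants with no follow-up contribute nothing. It also replaces the fitted line with visit-specific effects, and it too needs baseline to precede known allocation.

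The cost is a change of wording, with no new data, visits or participants. The small downside is reliance on that ordering. If it cannot be confirmed, the planned free-baseline model is the safer choice.

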However, to have power to address the secondary outcomes and because only a portion of the recruited Veterans will have anxiety and depression, we increased the sample size of 134 by 62.7% as described below, resulting in 218 Veterans to be recruited. Although all eligible participants will have diabetes-related distress, we expect depression and anxiety to be prevalent in 25% or more of participating Veterans. Fisher et al. found that 22.5% of those with high diabetes-related distress were clinically depressed. For these secondary outcomes, we initially calculated the sample size based on testing for a large effect size ($d = .80$) between the intervention and usual care groups at a single time point, using a two-group t test with a 0.05 two-sided significance level and power of 80%. Adjusting this to account for correlation among repeated measures results in 18.4 participants per group. Finally, adjustment for 30% attrition at 6 months results in a total needed of 27 per group. Therefore, we need to recruit 218 Veterans, of whom we expect 25% (54) to have anxiety and depression. Thus, we will have 80% power to detect a large effect size of .80 for the secondary outcomes of PHQ-8 and GAD-7. If we based the sample size for the secondary outcomes on detecting a medium effect size of .50, the required sample size of 134 patients would mean increasing the total to 536 patients, a number not feasible for this grant (25% of 536 patients = 134 with anxiety and depression).

In our prior work involving similar recruitment methods, we expect that approximately 7% of those referred to the study from VHA patient databases or community partners will be enrolled in the study (i.e. contact made, interested and eligible for the study). Therefore, we estimate that we will need to attempt to contact approximately 3,114 potential subjects in order to enroll 218 patients in the study.

G2. Data Analysis

Provide a description of your plan for data analysis. State the types of comparisons you plan (e.g. comparison of means, comparison of proportions, regressions, analysis of variance). Which is the PRIMARY comparison/analysis? How will the analyses proposed relate to the primary purposes of your study?

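### The logistic models for dichotomised DDS17, PHQ-8 and GAD-7 inherit time terms, but the plan names neither an analysis visit nor a method for within-participant correlation

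*Combined protocol and SAP*

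**What the plan says.** All references are to section G2 (Data Analysis) unless another section is named.

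- **Primary outcome, continuous DDS17.** A random coefficient model with a line for each participant. Its terms are treatment, referral source, SES, race/ethnicity, time (baseline, 3 or 6 months) and time-by-treatment. The interaction is the term of interest, and the treatment term is described as the baseline difference between groups.
- **Primary outcome, dichotomised DDS17** (below 3.0 versus 3.0 or more). Logistic regression: "Independent variables will be those for the linear regression models".
- **Secondary outcomes, continuous.** Said to be similar to the continuous primary analysis. Then: "We will then run linear regression models separately for each secondary outcome". The terms are introduced as: "The models will include terms for the intervention, time period, time-by-period interaction". The next sentence interprets the time-by-treatment interaction.
- **Secondary outcomes, dichotomised PHQ-8** (a decrease of 5.0 points from baseline) **and GAD-7** (below 10). Logistic regression: "The independent variables will be those described above for the linear regression models".
- **Resource use and newly used care.** Logistic regression with no time term and one outcome per participant over, or at, 6 months.

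For the three dichotomised scores, the plan names no analysis visit, random effect, GEE or robust variance. Section G1 sizes the trial partly on PHQ-8 and GAD-7, after an adjustment for the correlation of repeated measurements: "Thus, we will have 80% power to detect a large effect size of .80 for the secondary outcomes of PHQ-8 and GAD-7".

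**The concern.** A logistic model with time and time-by-treatment terms needs more than one record per participant. Records from one person are correlated, and ordinary logistic regression treats them as independent. The participant-level line in the primary model belongs to the continuous outcome, and the sentence linking the secondary analyses to it refers to the continuous primary analysis. Neither supplies a correlation method for a binary outcome.

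The carry-over of time terms cannot be dismissed as shorthand for a single-visit model. Where the authors want one record per participant, as for resource use and newly used care, they leave time out and state the 6-month window.

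What is at stake is the responder analyses, which are the ones described as showing clinically significant change. Depending on how an analyst fills the gap, the test is too conservative, too liberal, aimed at the wrong question, or impossible to fit. That choice would be made after the data are seen.

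**Working it through.** **1. The plan's own figures.** Section G1 gives two-sided alpha 0.05, power 80%, T = 2 follow-ups, correlation 0.5 and attrition 30%. The repeated-measures factor is [1 + (2 − 1) × 0.5]/2 = 0.75.

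- d = 0.50: 2 × [(1.96 + 0.84)/0.50]² = 62.79; × 0.75 = 47.09; / 0.70 = 67.28 per group. The plan states 67, so 134 in total.
- d = 0.80: 24.53; × 0.75 = 18.40; / 0.70 = 26.28, rounded up to 27 per group. The plan states 18.4 and 27. 54/0.25 = 216, against 218 stated (25% of 218 = 54.5).

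These reproduce. The sizing for PHQ-8 and GAD-7 counts on the repeated measurements, so the analysis should state how it uses them.

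**2. Assumptions for the binary models.** None of these is given in the documents.

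- 76 completers per arm (109 × 0.70 = 76.3).
- The same prevalence, about 50%, at every visit and in both arms under the null.
- The same correlation r between any two visits.
- r from 0.33 to 0.50. If the plan's 0.5 is the correlation of an underlying normal score cut at its median, then r = (2/π) × arcsin(0.5) = 0.33. If 0.5 is taken directly as the binary correlation, r = 0.50.

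**3. Interaction, stacked records, ordinary logistic regression.** The variance of an arm's log-odds at one visit is 1/(npq). The time-by-treatment contrast uses two arms at two visits:

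- assumed variance 4/(npq); true variance 4(1 − r)/(npq);
- ratio of assumed to true standard error = 1/√(1 − r), which is 1.22 at r = 0.33 and 1.41 at r = 0.50;
- type I error = 2[1 − Φ(1.96 × ratio)] = 1.7% and 0.6%.

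Simulation (2,000 replicates per setting) gave 1.1% and 0.6% with three records, and 1.5% and 0.7% with two. At r = 0.33 the Monte Carlo standard error is √(0.0166 × 0.9834/2000) = 0.29 percentage points, so 1.1% is best read as between 1% and 2%.

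**4. Treatment effect pooled over the two follow-ups, ordinary logistic regression.**

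- assumed variance 1/(npq); true variance (1 + r)/(npq);
- ratio = 1/√(1 + r), which is 0.87 and 0.82;
- type I error = 8.9% and 11.0%.

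Simulation gave 8.8% and 11.6%. With standard errors clustered on participant, all settings in steps 3 and 4 gave 4.4% to 6.0%.

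Prevalence cancels from both ratios when it is equal across visits and arms, so the 50% assumption matters less than r.

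**5. Each reading of the text.**

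| Rows per participant | What happens |
|---|---|
| Three (baseline, 3 and 6 months) | Standard errors as in step 3. For PHQ-8, a decrease from baseline is zero at baseline, so no baseline row can be an event. With categorical time, both arms' baseline log-odds are minus infinity and the interaction cannot be estimated. With linear time the model can converge, but it fits a line through a structural zero. |
| Two (3 and 6 months) | The interaction asks only whether the effect differs between 3 and 6 months, not whether the arms differ in improvement. Testing the pooled treatment term instead gives step 4. |
| One | Time and its interaction cannot be fitted, and the visit is not stated. |

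**The case against.** The strongest reply is that the authors plainly mean to respect the repeated measurements. The secondary analyses are tied to the primary random coefficient model. The primary-outcome text itself refers back to linear regression models when only the random coefficient model has been described, so linear regression appears to be a loose label for it. Section G1 adjusts PHQ-8 and GAD-7 for repeated-measures correlation.

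This stands for the continuous outcomes. From "We will then run linear regression models separately for each secondary outcome" a reader might infer that PHQ-8, GAD-7 and self-management scores will be analysed as if visits were independent. The documents do not support that. Likewise, the interaction misnamed in "The models will include terms for the intervention, time period, time-by-period interaction" is put right by the sentence that follows it. Both are matters of wording.

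Two other stronger readings also fail.

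- **That the errors generally favour the intervention.** The term the plan tests is time-by-treatment, and ignoring correlation makes that test conservative. The liberal error arises only if a treatment effect pooled over follow-ups is tested, whereas the plan describes its treatment term as a baseline difference.
- **That the PHQ-8 interaction is inestimable outright.** This needs both baseline rows and categorical time, and the plan specifies neither for the logistic model.

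The reply does not reach the dichotomised outcomes. A line fitted to a continuous score says nothing about how correlated binary records will be modelled. It is fair to add that these are supportive analyses and that the plan never says visits will be stacked without adjustment, so the harm depends on how the gap is filled.

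**Conclusion.** The point holds for the three dichotomised scores. The rule for choosing their independent variables does not work as written on any literal reading.

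If visits are stacked in ordinary logistic regression, type I error for the interaction falls from 5% to about 1.1% to 0.6% in simulation (1.7% to 0.6% in closed form), with loss of power. For a treatment effect pooled over the two follow-ups it rises to about 9% to 12%. These figures rest on equal prevalence of about 50%, equal correlation between visits of 0.33 to 0.50, and 76 completers per arm. They would change with other correlations, but the directions hold for any positive one.

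The sample size and the primary continuous analysis are untouched. The resource-use and newly-used-care models are sound in this respect, because they have one record per participant and no time term.

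**What to change.** For each of dichotomised DDS17, PHQ-8 and GAD-7, state one of the following in section G2:

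1. Logistic regression at one named visit (for example 6 months), with one row per participant, terms for treatment, SES, race/ethnicity and referral source, and no time terms.
2. A logistic GEE or mixed-effects logistic model on the 3- and 6-month rows only, clustered on participant, with the treatment contrast to be tested written out (for example the effect at 6 months, or the average over both visits).

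As a wording clarification only, say that the continuous secondary outcomes use the same random coefficient model as DDS17, and rename the listed interaction time-by-treatment.

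The cost is a few sentences and a standard software procedure. No new data, visits or participants are needed, and the sample size does not change.

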Will pregnant women and/or fetuses (as described in 45 CFR 46 Subpart B) be enrolled in the research?

No

E4. Neonates

Will neonates of uncertain viability or nonviable neonates (as described in 45 CFR 46 Subpart B) be enrolled in the research?

No

E5. Children

Will children be enrolled in the research?

No

Section F: Design/Procedure

F1. Design

Select one category that most adequately describes your research:

z.r) Randomized, Efficacy Study -- Surgical Techniques/Interventions

Discuss the research design including but not limited to such issues as: probability of group assignment, potential for subject to be randomized to placebo group, use of control subjects, etc.

Overview. The goal of the study is to conduct and evaluate a time-limited, Veteran peer-support specialist-led navigation intervention on diabetes-specific outcomes, mental health outcomes, and use VHA or community care in Veterans with DM and clinically significant diabetes-related distress. We will evaluate the outcomes of the intervention in a randomized trial comparing the intervention to usual care. The proposed work is informed by an established and ongoing partnership between VHA researchers and clinicians, individual Veterans, and representatives of Veteran Service Organizations (VSOs)/Community Based Organizations (CBOs) serving Veterans. These key partners have been working together for more than a year, as described above, and will collaborate on all aspects of the research, as detailed below. Study design. This is a single-blind, parallel group, randomized trial of a 3-month peer-navigation intervention for Veterans with DM and elevated levels of diabetes-related distress. Participants will be assigned at random (see below) to the intervention (peer navigation with follow-up) or usual care (print materials and encouragement to continue follow-up with health care providers). Assessment of primary, secondary and intermediate end points will occur preintervention at baseline and postintervention at 3 and 6 months.

Participants. We plan to recruit 218 participants (1:1 allocation) over 31 months (7/month). Central to the design of this trial is the recruitment of Veterans who are VHA users and Veterans who are not. We will screen at our local VHA medical center (MEDVAMC) and established community partnerships, including government agencies, CBOs, and VSOs as described above.

Inclusion Criteria:

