Patients will be eligible to participate in the study if they meet the following criteria:

(1) Veteran (2) Diagnosis of type 2 diabetes mellitus, per self-report (3) Moderate diabetes-related distress (Diabetes Distress Scale [DDS2] mean score of 3 or greater)

Exclusion Criteria:

(1) Lack of reliable access to a telephone (2) Cognitive, sensory, or other impairment that prevents use of a telephone (3) Current participation in another diabetes-related counseling or self-management program

F2. Procedure

Upon providing informed consent, participants will be randomized in blocks of 6 or 8, based on referral source (MEDVAMC and non-MEDVAMC). At the initial screen, the study staff will confirm eligibility. Veterans will be screened for distress using the 2-item screening version of the Diabetes Distress Scale. Veterans with a mean score of 3 or more will be eligible to continue. Veterans who are eligible and wish to participate further will be scheduled for a telephone baseline assessment. They will be mailed a cover letter, informed consent document without signature lines, and copies of baseline assessment instruments. A member of the study team will call and review the consent documents before final enrollment and completion of the baseline assessment.

Usual care. Veterans randomized to the usual care condition will be encouraged to follow-up with their primary care provider and/or specialty providers for management of their health conditions. They will receive a packet of printed information that includes a list of self-management support resources in the VHA and the local community, but no specific recommendations or referrals. The list will be updated periodically with similar resources as needed.

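### The PHQ-8 responder analysis names no baseline population, so participants scoring 0 to 4 at baseline are fixed non-responders in both arms (minor)

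*Combined protocol and SAP*

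**What the plan says.** All references are to the combined protocol and SAP.

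- **G2 Data Analysis, secondary outcomes.** The response threshold is "A 5.0-point decrease in the value of PHQ-8 will be considered a minimally clinically important change". For anything smaller, "decreases of less than 5.0 points from baseline will be coded as not having achieved clinically significant change". The logistic model takes over the terms of the linear models: "The independent variables will be those described above for the linear regression models". Those terms are intervention, time, their interaction, SES, race/ethnicity and referral source. No baseline PHQ-8 term, minimum baseline score or subset is named.
- **F1 Design, inclusion criteria.** The only symptom criterion is "3) Moderate diabetes-related distress (Diabetes Distress Scale [DDS2] mean score of 3 or greater". There is no PHQ-8 or depression threshold.
- **G1 Sample Size.** The plan recognises that "only a portion of the recruited Veterans will have anxiety and depression", and that "we expect depression and anxiety to be prevalent in 25% or more of participating Veterans". It bases the PHQ-8 and GAD-7 power on that portion: "we need to recruit 218 Veterans, of whom we expect 25% (54) to have anxiety and depression".
- **G2, care utilisation.** For new use of VHA care, the plan limits the analysis to participants who were not using VHA services at baseline, that is, to those able to have the event. Community care is handled in the same way.

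**The concern.** A responder defined by a fall of 5 points needs a baseline of at least 5. Participants are selected for diabetes distress, not depression, and the plan itself expects many of them not to be depressed. Some can be expected to start at 0 to 4, and as the rule is written their result is known before treatment starts.

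Two things are at stake. The reported response rates would mix people who did not improve with people who had no room to improve. The comparison would also carry observations that hold no information about treatment, which lowers power. In addition, the population used to justify PHQ-8 power in G1 (about 54 Veterans) is not carried into the analysis in G2, so a reader cannot tell which population the responder result describes.

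**Working it through.** **1. The plan's own figure.** G1 gives d = 0.80, two-sided alpha 0.05, power 80%, T = 2 follow-ups, correlation 0.5 and 30% attrition.

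- Per group: 2 × ((1.96 + 0.84)/0.80)² = 24.53 (unrounded z values)
- Repeated-measures factor: (1 + 0.5)/2 = 0.75, and 24.53 × 0.75 = 18.40
- Attrition: 18.40/0.70 = 26.28, rounded up to 27 per group, 54 in total
- Total: 54/0.25 = 216, against the stated 218 (134 × 1.627 = 218.0)

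The figure reproduces and is not in question. It shows that PHQ-8 power was worked out for about 54 symptomatic participants.

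**2. The floor.** The documents do not give the PHQ-8 range, so a minimum of 0 is assumed. The largest possible fall from baseline b is then b. For b = 0 to 4 it is at most 4, below the 5.0 required.

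**3. Effect on the rates.** Let q be the share below 5, and let p_C and p_T be the response rates among those able to respond. Coding everyone gives p_C(1 − q) and p_T(1 − q), a risk difference of (1 − q)(p_T − p_C), and a ceiling of 1 − q in each arm.

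**4. Effect on power.** Completers per arm: 218 × 0.70/2 = 76.3, taken as 76. Restricting leaves 76(1 − q) per arm. Power for two proportions uses the normal approximation:

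Φ( [|p_T − p_C| − 1.96√(2p̄(1 − p̄)/n)] / √([p_T(1 − p_T) + p_C(1 − p_C)]/n) )

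Both q and the response rates are assumptions.

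| Response among those able | q | Rates, everyone coded | Odds ratio, everyone | Power, everyone | Power, baseline ≥ 5 |
|---|---|---|---|---|---|
| 30% vs 50% | 0 | 30% vs 50% | 2.33 | 0.72 | 0.72 |
| | 0.2 | 24% vs 40% | 2.11 | 0.56 | 0.62 |
| | 0.4 | 18% vs 30% | 1.95 | 0.41 | 0.50 |
| | 0.6 | 12% vs 20% | 1.83 | 0.27 | 0.35 |
| 20% vs 40% | 0 | 20% vs 40% | 2.67 | 0.77 | 0.77 |
| | 0.2 | 16% vs 32% | 2.47 | 0.64 | 0.68 |
| | 0.4 | 12% vs 24% | 2.32 | 0.49 | 0.55 |
| | 0.6 | 8% vs 16% | 2.19 | 0.33 | 0.40 |

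In the restricted analysis the odds ratio stays at 2.33 or 2.67. The gain in power is about 4 to 9 points.

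**5. The same effect as sample size.** With mean response p among those able to respond, the squared ratio of the test statistics (restricted over everyone) is (1 − p(1 − q))/(1 − p).

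- q = 0.2, p = 0.3: 0.76/0.70 = 1.09
- q = 0.3, p = 0.4: 0.72/0.60 = 1.20
- q = 0.5, p = 0.5: 0.75/0.50 = 1.50

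The last case needs half the sample at the floor and also a 50% response among the rest. In a simulated mix (152 participants, 3,000 runs) with 48% below 5, response was 6% vs 15% in everyone and 12% vs 29% at baseline 5 or more. There p = (0.12 + 0.29)/2 = 0.205, and the ratio is (1 − 0.205 × 0.52)/0.795 = 1.12. The simulated powers agree: 42% against 46% when the effect was in symptomatic participants, and 57% against 62% when it was proportional.

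**The case against.** Several points on the other side are sound.

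- **No bias.** Randomisation makes the share below 5 about equal in the two arms. The proportion responding among all participants is a valid contrast, only a diluted one. A reader might infer a biased test or an inflated false-positive rate; nothing in the documents supports that.
- **Everyone is coded only by inference.** No sentence says so; it follows from the absence of a restriction. G1 counts only about 54 symptomatic Veterans for PHQ-8 power, so a subset may have been intended. Against that, G2 names its subsets for care use, and names none here. The text therefore needs reconciling whichever was meant.
- **The plan does not claim to estimate improvement among depressed Veterans.** It asks whether the groups differ in reaching clinically significant change. A reader might also infer that a cut at 5 would supply the rate among depressed Veterans. It would not: 5 is the arithmetical minimum for a response, and someone starting at 5 must reach 0.
- **The share below 5 is unknown.** It is tempting to take the 75% outside the expected 25% prevalence as the share at the floor. A participant without clinical depression may still score 5 or more, so that step fails.
- **Narrow scope.** The same paragraph of G2 counts GAD-7 below 10 as improvement with no baseline condition. A change to PHQ-8 alone leaves the two responder analyses on different populations, which the write-up should make clear.

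These points limit the size and severity. They do not remove the fact that, as written, some participants cannot respond.

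**Conclusion.** The point holds as a minor one. G2 does not say who enters the PHQ-8 responder analysis, and read as it stands it codes participants with a baseline of 0 to 4 as non-responders whatever happens to them. Response rates and the risk difference shrink by the share below 5, and the odds ratio moves towards 1. The power cost is about 4 to 9 points for assumed shares of 20% to 60% and assumed response of 20% vs 40% or 30% vs 50%. In the simulated mix the gain from restricting is worth about 12% of effective sample.

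A larger figure, such as 50% more effective sample, needs extreme assumptions that the documents do not support. The direction is certain for any share above zero, given a scale minimum of 0; the size is not, because no PHQ-8 distribution is given. The primary DDS17 analysis is untouched, and the continuous PHQ-8 model does not use the responder rule.

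**What to change.** In G2, secondary outcomes, before outcome data are examined:

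1. Define the PHQ-8 responder comparison on participants with baseline PHQ-8 of 5 or more, and report the number excluded in each arm. The baseline score is collected before the intervention, so this keeps the randomised comparison.
2. Describe the result as applying to participants able to respond, not to depressed Veterans.
3. Reconcile this with G1 by also reporting the symptomatic subset assumed there, and state the score that defines it, since G1 gives none. With 54 recruited and 30% attrition this is 54 × 0.70 = 37.8 completers, about 19 per arm. By the power formula above, 19 per arm gives power of 0.24 for 30% vs 50% and 0.26 for 20% vs 40%, so the subset is better reported descriptively.
4. Keep the continuous PHQ-8 model on all participants.

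The cost is a sentence or two in the plan, a smaller denominator, and a narrower population for this one analysis. The smaller denominator does not cost power for this contrast, because the participants removed have an outcome that is already fixed.
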